8.3.3	Analysis of Safety Endpoints.....	18
8.4	Hypothesis and Sample Size Calculation.....	19
8.5	Missing Data	19
9.0	Ethical Considerations	19
9.1	Ethical Approval	19
9.2	Protocol Amendments	19
9.3	Informed Consent	19
10.0	Risk – Benefit Analysis	20
10.1	Study Related Risks	20
10.2	Study Related Benefits.....	20
11.0	Monitoring Procedures	20
11.1	Source Documentation	20
11.2	Direct Access	21
11.3	Site Qualification Visit	21
11.4	Activities Prior to Study Initiation.....	21
11.5	Site Initiation Visit.....	21
11.6	Interim Monitoring Visits.....	21
11.7	Sponsor Audits and Regulatory Inspection	22
11.8	Closeout Visit	22
11.9	Documentation of Monitoring Visits	22
12.0	Data Handling and Record Keeping Requirements	22
12.1	Data Recording and Record Retention.....	22
13.0	Deviations from Protocol.....	23
13.1	Protocol Deviation Reporting Requirements.....	23
14.0	Publication Policy.....	23
14.1	Investigator Publication	23

Abbreviations and Definitions:

AE	Adverse Event
ADE	Adverse Device Effect
CAPA	Corrective and Preventive Action
CoCr	Cobalt Chrome
CRO	Contract Research Organization
CRF	Case Report Form
CSR	Clinical Study Report
CT	Computed Tomography
CTA	Clinical Trial Agreement
CV	Curriculum Vitae
EC	Ethics Committee
EOS	End of Study
FDA	Food and Drug Administration
FU	Follow-Up
GCP	Good Clinical Practice
ICF	Informed Consent Form
ICH	International Conference on Harmonisation of Technical Requirements for Registration of Pharmaceuticals for Human Use
ID	Identification Number
IRB	Institutional Review Board
ITT	Intent-to-Treat Population
MARS MRI	Metal artifact reduction sequence (MARS) magnetic resonance imaging (MRI)
PI	Principal Investigator
PP	Per Protocol
QA	Quality Assurance
QC	Quality Control
SADE	Serious Adverse Device Effect
SAE	Serious Adverse Event
SAP	Statistical Analysis Plan
SDV	Source Data Verification
SMF	Short Modular Femoral
SOP	Standard Operating Procedure
THA	Total Hip Arthroplasty
USADE	Unanticipated Serious Adverse Device Effect

Protocol Synopsis:

Study Title	A Safety Follow Up Study in Australian Subjects implanted with the SMF Short Modular Femoral Stem Hip System
Short Title	SMF modular stem safety follow up study
Sponsor	Smith & Nephew Surgical Pty Ltd [name]
Study Type	Post Market Study
Study Device	SMF Short Modular Femoral Stem
Indications	Total Hip Arthroplasty
Study design	A single center, single arm, consecutive series study
Study Objective	The primary objective of this study is to provide safety data for the SMF Short Modular Femoral Stem Hip System up to a follow up period of 20 years post implantation
Primary Endpoint	Safety Data based on the following assessments: 
 ▪ Whole blood cobalt and chromium ion levels collected annually for symptomatic subjects and every 3 years for non-symptomatic subjects ▪ Metal artifact reduction sequence (MARS) magnetic resonance imaging (MRI) or Computed Tomography (CT) in subjects with whole blood cobalt and/or chromium > 7 parts per billion (ppb)
Secondary Endpoints	
 ▪ Standard of Care Radiographic assessments ▪ HOOS JR Hip Questionnaire ▪ Revision of any component of the study device for any reason ▪ Adverse events assessment
Length of Study	Approximately Twelve Years. Subjects have been implanted with the SMF Device in 2009 and 2010 at the investigational site. The Baseline visit will be determined as the first visit to site after Ethics approval for the study has been received. This will be approximately 8-9 years post implant. Enrolled subjects will be followed up to 20 years post SMF implant
Number of Sites	1 site (Australia)
Sample Size	Up to 26 subjects based on feasibility only
Inclusion Criteria	
 ▪ Subject has undergone primary total hip arthroplasty with the SMF Short modular femoral stem at the study site and still has the original implant at the time of Ethics Committee (EC) approval of the study ▪ Subject is willing and able to participate in follow-up visits at the study site

Exclusion Criteria	
 ▪ The Subject, in the opinion of the PI, has an emotional or neurological condition that would affect their ability or willingness to participate in the study including mental illness, mental retardation, drug or alcohol abuse ▪ Subject is known to be at risk for lost to follow-up or failure to return for scheduled visits
---------------------------	--

1.0 Background and Study Rationale

This clinical study will be performed in compliance with the ethical principles of the Declaration of Helsinki; ISO 14155:2011 Clinical investigation of medical devices – Good Clinical Practice; ICH-E6 and the approving Ethics Committee Guidelines.

In compliance with post-marketing surveillance obligations, Smith & Nephew continually monitors the performance of its products. During a recent review of product complaints received by Smith & Nephew and clinical study data associated with the modular hip prostheses, the Sponsor observed a rate of complaints higher than comparable monolithic hip prostheses. Based on an analysis of available data sets, Smith & Nephew considers that patients implanted with the modular neck hip prostheses may be at greater risk of revision surgery than with comparable monolithic products. For this reason, on a precautionary basis Smith & Nephew issued a voluntary field safety corrective action for the modular neck hip prostheses. With this voluntary market removal of the modular neck, SMF modular stems were removed from the market in November 16, 2016.

The purpose of the current investigation is to provide safety data for the SMF Short Modular Femoral Stem Hip System in implanted subjects. The safety data will be based on assessments of whole blood cobalt and chromium ion levels and Metal artifact reduction sequence (MARS) magnetic resonance imaging (MRI) or Computed Tomography (CT) in subjects with cobalt and/or chromium > 7parts per billion (ppb).

2.0 Study Objectives

The primary purpose of this study is to provide safety data on the SMF Short Modular Femoral Stem THA system with regards to laboratory, radiographic and clinical outcomes in implanted patients.

3.0 Study Design

This is a single arm, consecutive series study to collect relevant clinical, laboratory and radiological data in up to 26 subjects, who have been implanted with the SMF Short Modular Femoral Stem THA system at 1 site in Australia.

The Baseline visit will be determined as the first visit to site after Ethics approval for the study has been received. This will be approximately 8-9 years post implant. Enrolled subjects will be followed up to 20 years post SMF implant. The Baseline visit assessments are described in Section 5.5 and 5.6. Post Baseline, the study will allow for metal ion assessments every 3 years for asymptomatic subjects and annual assessments for subjects with pain, swelling, and/or functional limitations if assessed by the Principal Investigator to be related to the SMF implant, having ruled out all other probable causes for the subject. If the subject has elevated whole blood cobalt or chromium (defined as >7ppb) a MARS MRI or CT will be obtained. These types of imaging techniques are aimed at

detecting inflammatory degenerative evolution of periarticular soft tissues including pseudo-tumors. A functional Questionnaire, HOOS JR Questionnaire will be completed at all patient site visits.

3.1 Primary Endpoint

- Safety assessment of the SMF Short Modular Femoral Stem implanted Subjects using Metal Ion Analysis and MARS MRI/ or CT at Baseline and at protocol scheduled visits at the 1 yearly or at the 3 yearly time point as per the study schematic Table 1.

Metal Ion Level assessment

- All Subjects at Baseline and every three years afterwards will have whole blood collected for metal ion testing of whole blood cobalt and chromium
- Symptomatic subjects with pain, swelling, and/or functional limitations if assessed by the PI to be related to the implant will have whole blood collected for metal ion testing of cobalt and chromium annually

MARS MRI/CT

- Subjects with whole blood cobalt and/or chromium > 7 ppb will have MARS MRI (or CT if MRI is contraindicated) performed

3.2 Secondary Endpoints

- Revision of any component for any reason
- Standard of Care Radiographic assessments
 - Loosening as indicated by radiolucencies > 2mm
 - Evidence of surface wear or particulate debris generation as indicated by early osteolysis, implant migration, or other clinical or radiographic abnormalities such as pseudo tumors or corrosion
- HOOS JR Questionnaire
 - The score will be calculated to assess clinical efficacy
- Adverse Events assessment
 - Safety will be evaluated by assessing the frequency and nature of adverse events as defined in the Safety Reporting section

4.0 Study Device

4.1 Device Description

The study device in this study is a SMF Short Modular Femoral Stem.

The **SMF Short Modular Femoral Stem** is described below:

A. Femoral Hip Stem

The femoral stem is a straight, tapered and proximally loading stem designed to match the geometry of the femur. The stems are proportionally sized and shaped in sizes 1 through 9. The stem is made of coated titanium alloy and is matched with a polished modular neck. Each femoral stem is proximally coated with Smith & Nephew's StikTite porous coating.

B. Modular Neck

The short mini stem mates with a modular neck designed with various offsets. The modular neck is manufactured from polished Cobalt Chrome. All modular necks have a 12/14 taper and are compatible with various heads.

4.2 Device Accountability

As this is a post-surgical safety data collection study, no device accountability will be performed. Device revisions and device complaints will be followed up as per Sponsor guidelines. Every effort will be made to return devices if applicable and to follow up all device complaints according to device safety processes and Sponsor guidelines.

5.0 Study Population

5.1 Screening and Enrollment

Subjects will be screened according to the study inclusion and exclusion criteria. Subjects meeting the eligibility criteria will be contacted by the PI and be invited to participate in the study.

All potential subjects who undergo the screening process and are excluded from the study will have the reason for exclusion documented on a Screening and Enrollment Log. The reasons for exclusion may include refusal to participate in the study visits, lost to follow-up or that the subject is deceased.

Subjects will be assigned consecutive Subject Identification (ID) numbers, by date of PI contact to discuss study participation.

5.2 Informed Consent

The study will be explained to the eligible subject by the PI and if the subject agrees to participate, the informed consent process will be conducted. The subject will be given time to discuss study participation and ask questions. The informed consent form must be signed before any study related procedure is performed.

The informed consent process will be documented in the subject's medical record and in the study Case Report Forms (CRFs). The informed consent form (ICF) will be placed in the subject file and a copy will be provided to the subject.

5.3 Subject Inclusion Criteria

Subjects must meet the following inclusion criteria:

- The Subject has undergone primary total hip arthroplasty with the SMF Short modular femoral stem at the study site and still has the original implant at the time of Ethics Committee (EC) approval of the study
- Subject is willing and able to participate in follow-up visits at the study site

5.4 Subject Exclusion Criteria

Subjects meeting any of the following exclusion criteria will be excluded from study participation:

- Subject, in the opinion of the PI, has an emotional or neurological condition that would affect their ability or willingness to participate in the study including mental illness, mental retardation, drug or alcohol abuse
- Subject is known to be at risk for lost to follow-up, or failure to return for scheduled visits

5.5 Data Collection

All subjects will have a Baseline data collection and at the yearly or 3 yearly visits as described below and in the study schematic Table 1. Data will also be collected at unscheduled visits which will be conducted if the subject experiences a device related adverse event in between scheduled visits.

5.5.1 Baseline Visit

- Informed Consent
- Implant and Joint Status
- Operative Date
- Demographics
- Medical History and Concomitant Medication
- HOOS JR Questionnaire
- Radiographic evaluation
- Adverse events assessment
- Metal Ion Level assessment
 - Whole blood will be collected for metal ion testing of cobalt and chromium
- MARS MRI/CT
 - Subjects with whole blood metal ion levels > 7 ppb will have a MARS MRI performed (or CT if the MRI is contraindicated)
- Study termination, if applicable

5.5.2 1 Year/3 Year Visits (\pm 3M) up to 20 years post implant Follow Up

Annual visit schedule for symptomatic subjects and 3 Year visit schedule for non-symptomatic subjects

- Implant Status

- Demographics
- Medical History and Concomitant Medication
- HOOS JR Questionnaire
- Radiographic evaluation
- Adverse events assessment
- Metal Ion Level assessment
 - Whole blood will be collected for metal ion testing of cobalt and chromium
- MARS MRI/CT
 - Subjects with metal ion levels > 7 ppb will have a MARS MRI performed (or CT if MRI is contraindicated)
- Study termination, if applicable

5.5.3 Unscheduled Follow-up Visit

The unscheduled study visit will be determined by the PI for safety follow up. The visit assessments will be as required for safety follow up of the individual subject.

5.6 Table 1: Study Schematic

The intervals and schedule of events for this study are provided in Table 1.

Schedule of events	Screening/ Telephone Call	Baseline Visit	1 Year visit for symptomatic subjects/3 Year visit for non-symptomatic subjects (± 3M)	EOS Visit (20 years post SMF Implant procedure) (± 6M)	Unscheduled visit
Subject Status verification	X ¹				
Informed Consent		X			
Inclusion/Exclusion Criteria		X			
Implant Status	X ¹	X	X	X	X
Operative Date		X			
Demographics		X			

Schedule of events	Screening/ Telephone Call	Baseline Visit	1 Year visit for symptomatic subjects/3 Year visit for non-symptomatic subjects (\pm 3M)	EOS Visit (20 years post SMF Implant procedure) (\pm 6M)	Unscheduled visit
Medical History and Concomitant Medication		X	X	X	X
HOOS JR Questionnaire		X	X	X	X
X-ray Assessments		X ²	X ²	X ²	X ³
Adverse Events Assessment		X	X	X	X ³
Metal Ion level Assessments		X	X	X	X ³
MARS MRI /CT		X ³	X ³	X ³	X ³
End of Study		X ³	X ³	X	X ³

X¹ Verification of Eligibility via telephone contact to determine patient and implant status

X² X Ray Assessments/Radiographs will be in line with standard of care

X³ If Applicable

HOOS JR: The Hip Osteoarthritis Outcomes Score Junior is a validated short questionnaire that the patient completes focusing on joint pain, stiffness, and function relating to daily living.

6.0 Subject Completion and Discontinuation

6.1 Conditions for Subject Termination

All reasonable efforts should be made to retain all consented subjects out to the 20 year post-implant study duration. There are multiple reasons a subject may terminate participation from the study. For each case, the reason will be documented on the Study Termination CRF detailing the circumstances leading to the withdrawal.

6.1.1 Screen Failure

- Subjects known to have received the SMF Short Modular Femoral stem as a total hip arthroplasty who does not agree to the prospective on-site study visits
- A Subject who has undergone a SMF Short Modular Femoral Stem THA but does not meet all inclusion/exclusion criteria and therefore is not enrolled in the study
- A Subject is not enrolled by the Investigator for any reason
- Subject does not give consent to provide any information for the purposes of the study when approached for participation

The reasons for the screen failure subjects will be recorded in the Site's Screening and Enrollment Log.

6.1.2 Voluntary Withdrawal

Study participation is voluntary and subjects may withdraw their participation from the study without giving reason for doing so. The withdrawal will be documented in the subject's CRF.

6.1.3 Lost to Follow-Up

Study personnel must make a reasonable effort to contact the subject and document the contact attempts according to the site's policies prior to declaring a subject to be lost to follow-up. Copies of all attempts to reach the subjects per regular mail, email and/or any other means should be documented in the subject's medical record and the CRF.

6.1.4 Study Termination by Investigator/Sponsor

The Investigator may withdraw subjects from the study for many reasons, including but not limited to the following:

- subject noncompliance to study visit schedule
- subject lost to follow-up
- Investigator or the Sponsor terminates the study for any reason

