8.5 Missing Data

A complete accountability report, along with the explanation for lost-to-follow-up, death, revision, and withdrawn subjects, will be provided in the Clinical Study Report (CSR). A complete list of the informative/non-informative missing data will be also be provided in the CSR. Due to the nature of the study, no imputation of missing data is planned.

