13.0 Deviations from Protocol

A protocol deviation is an instance of failure, intentionally or unintentionally, to follow the requirements of the protocol. Protocol deviations include but are not limited to: deviations from inclusion/exclusion criteria, missed or otherwise inadequate data collection, study visits outside the window, and violation of GCP guidelines.

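### Section 6.1.4 allows withdrawal for missed visits with no threshold, no prior contact step and no later check of implant status, so a later revision in a reachable subject could go uncounted

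*Combined protocol and SAP*

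**What the plan says.** Section 6.1.4 gives the investigator a discretionary and open-ended power: "The Investigator may withdraw subjects from the study for many reasons, including but not limited to the following". One listed ground is "subject noncompliance to study visit schedule". Loss to follow-up is a separate item in the same list, so the noncompliance ground also reaches subjects who can still be contacted.

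Three other provisions bear on the same subject:

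- Section 6.1 sets the retention aim: "All reasonable efforts should be made to retain all consented subjects out to the 20 year post-implant study duration". It goes on to say "There are multiple reasons a subject may terminate participation from the study", with the reason recorded on the Study Termination CRF.
- Section 13.0 lists "missed or otherwise inadequate data collection, study visits outside the window" among protocol deviations.
- Section 6.1.3 requires documented contact attempts before a subject is declared lost. Section 6.1.4 has no matching step for noncompliance.

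On the analysis side, section 8.3.2 reports revision as the frequency at end of study, as a percentage of the full analysis set. Section 8.5 promises an accountability report that covers withdrawn subjects and says "no imputation of missing data is planned". Section 7.0 keeps adverse device effects that occur after study completion out of the study database, and does not say what study completion means for a withdrawn subject.

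**The concern.** The study observes an implant already in place and gives no study treatment. Withdrawing a non-attender therefore removes no exposure; it only ends observation. Section 1.0 explains that the sponsor considers patients with modular necks may be at greater risk of revision, so revision status out to 20 years is among the most informative things the study can collect.

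A subject who misses visits may still answer the telephone, and the site may still hold records. If participation ends at that point, a revision some years later leaves no trace in the study data. Subjects who stop attending may differ from those who continue, and the visit schedule itself exposes symptomatic subjects to the rule more often. In a series of at most 26, a few such subjects could move the revision percentage noticeably, and always downward.

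**Working it through.** The documents state no figure to reproduce: 26 is a feasibility ceiling, and no dropout rate is given. The check is a comparison of the text followed by illustrative arithmetic.

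**1. Which rule governs a missed visit?** Section 13.0 makes it a deviation. Section 6.1.4 makes noncompliance with the schedule a possible ground for withdrawal. The two can coexist, but nothing says when a logged deviation becomes a withdrawal. A reachable non-attender can be withdrawn with less documented effort than section 6.1.3 demands for an unreachable one.

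**2. What is collected afterwards?** No route is described. Section 7.2 passes unresolved adverse events to standard of care when participation ends. Yet the protocol already has the needed tools. Table 1 uses a telephone call at screening: "Verification of Eligibility via telephone contact to determine patient and implant status". Section 6.1.5 drops contraindicated procedures in pregnancy but keeps the subject under follow-up.

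**3. Who is most exposed?** Baseline is about 8 to 9 years after implant and follow-up ends at 20 years, so 20 − 9 = 11 to 20 − 8 = 12 years. Annual visits number k = 11 to 12; three-yearly visits number k = 3 to 4. The ratio is 12/4 = 3.0 to 11/3 = 3.7. With an assumed miss probability m per visit, independent across visits and with symptom status constant throughout, the chance of at least one missed visit is 1 − (1 − m)^k:

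| m (assumed) | Symptomatic, k = 11–12 | Asymptomatic, k = 3–4 |
|---|---|---|
| 2% | 20–22% | 6–8% |
| 5% | 43–46% | 14–19% |
| 10% | 69–72% | 27–34% |

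**4. Effect on the revision percentage.** Take N = 26 and read the full analysis set as all enrolled subjects (section 8.1 defines only ITT and PP populations). If r revisions are seen and w subjects are withdrawn with unknown later status, the planned figure is r/26, and the true one lies between r/26 and (r + w)/26. Both r and w are assumptions.

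| w | r = 0: planned → upper bound | r = 2: planned → upper bound |
|---|---|---|
| 1 | 0% → 1/26 = 3.8% | 7.7% → 3/26 = 11.5% |
| 2 | 0% → 2/26 = 7.7% | 7.7% → 4/26 = 15.4% |
| 3 | 0% → 3/26 = 11.5% | 7.7% → 5/26 = 19.2% |
| 5 | 0% → 5/26 = 19.2% | 7.7% → 7/26 = 26.9% |

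The exact (Clopper-Pearson) 95% intervals are 0 to 13.2% for 0/26 and 0.9 to 25.1% for 2/26. They describe sampling error only and do not widen for unknown status. With w = 5 the upper bound lies outside the interval in both columns; with w = 1 it lies inside in both.

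**The case against.** Several stronger readings are tempting, and the documents do not support them.

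- A reader might infer that a missed visit is solely a deviation, so that 6.1.4 contradicts 13.0. Section 13.0 does not say so, and a deviation can be logged before a later withdrawal.
- A reader might infer that every subject must be retained. Section 6.1 asks for reasonable efforts and expects terminations.
- A reader might infer that withdrawal discards data. No passage removes data already collected, and section 8.5 accounts for withdrawn subjects. Existing data could be left out through the PP population's undefined major violations (section 8.1), but that is a separate question.

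The opposing case goes further. The power is discretionary, visits have a ±3 month window, and nothing directs withdrawal after one absence. Eligibility requires willingness and ability to attend on site, and the primary endpoint needs a blood draw that a telephone call cannot replace. Section 4.2 follows device revisions and complaints under sponsor guidelines, so later events are not wholly invisible. Deleting the bullet would leave the power intact, because the list is open-ended. The values of r and w have no source in the documents, and the upper bounds require every withdrawn subject to have been revised.

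All of that stands, and it limits the point. It does not supply a route from a later revision to the study database, and it does not say how section 8.3.2 treats unknown status.

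**Conclusion.** The point holds as a gap and an unresolved tension, not as a contradiction. A reachable subject can be withdrawn for missing visits under no stated limit, and later revisions and device-related events would then have no described path into the study data. Unless the planned SAP (section 8.2) says otherwise, the crude percentage treats that subject as unrevised, so any error in the revision figure is downward.

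The size is at least 3.8 percentage points for each withdrawn subject who is later revised, in a series of at most 26. The larger bounds illustrate what could happen and do not forecast it. Selective loss is plausible from the visit counts but is not shown by the documents. The frequency of use is unknown and the study is descriptive, so this is a modest, inexpensive improvement.

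**What to change.** - **Section 6.1.4:** state that missed visits alone are not a ground for withdrawal, and that they are logged as deviations under section 13.0. Deleting the bullet is not enough.
- **Follow-up of non-attenders:** for subjects who stop attending without withdrawing consent, record implant status (revised or not, component, date), vital status and device-related events by telephone or from site records, at each due visit and at 20 years. Add a line to the consent form and CRF to cover this.
- **Section 8.3.2 and the SAP:** report the number of subjects with unknown revision status at 20 years beside the revision percentage, and do not count them as unrevised.

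The cost is a few calls or record checks, one CRF and consent line, and more subjects on the books with incomplete visits. Ion and imaging results for missed visits stay missing, and revisions done elsewhere may not appear in site records if the subject cannot be reached. The change narrows the uncertainty and does not guarantee its removal.
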